1.4 Purpose of Study/Potential Impact

Heavy alcohol use among young adults is an important public health problem. Alcohol use disorder (AUD) onset peaks during young adulthood (i.e., 18-25).[1] Young adults report the highest rates of heavy drinking,[2] which puts them at increased risk for substantial negative consequences such as accidental injury, (i.e., the primary cause of death in this group),[3-5] and makes them a priority population for intervention.

Current alcohol prevention and early intervention efforts for young adults have limitations. Effective alcohol interventions are available for young adults but tend to have small effects on drinking.[6-8] Most young adults do not seek help for their drinking, often due to low perceived need.[9-12] Moreover, young adults are least likely to have medical visits with a healthcare provider[13, 14] where they could receive effective alcohol preventive services.[15] There are also gaps in access. While college students tend to have more support services, particularly free and/or low cost options, their non-college same aged peers do not. [16]

Effective strategies need to better align with young adults' health practices and preferences. Though alcohol help-seeking may be low among young adults, they are open to receiving help for other health behaviors such as sleep and exercise. [17-19] These health topics may provide alternative gateways for intervening on alcohol use, bypassing the need for self-identification. Young adults, a generation that grew up with the convenience of technology, are also increasingly turning to mobile and digital health tools. [20-22]

Mobile health interventions that embed brief alcohol intervention content may offer a novel solution. We developed and conducted a preliminary test of a mobile sleep intervention for heavy-drinking young adults for engaging them in treatment and reducing their drinking (see Preliminary Studies).[19] We targeted sleep because poor sleep is common among heavy-drinking young adults [23, 24] and an AUD risk factor, [25-31] young adults are interested in their sleep health, [32] and sleep interventions address alcohol use as standard care, thereby providing a practical opportunity to embed alcohol content. Within the last decade, there has also been an explosion in the importance of sleep [33-35] and technology options for improving it. [36, 37] Qualitative data from this pilot (N=42) and our ongoing R34-funded follow-up study (96/120 enrolled to date) generated new hypotheses. Specifically, subjects expressed an interest in receiving feedback about other health outcomes besides sleep and indicated that feedback showing the negative effects of alcohol and/or sleep on health biomarkers would further motivate them to change their behavior.

New sensor technology, that measures heart rate variability, a non-invasive, robust biomarker of health, shows potential for alcohol prevention and early intervention. In addition to sleep, there has been a rapid increase in the importance of heart rate

variability (HRV) as a useful biomarker for tracking health and well-being, due in large part to new photoplethysmography (PPG) sensors and mobile apps that capture HRV, resting heart rate (RHR), and sleep. [38] HRV reflects cardiac control of the autonomic nervous system (ANS). [38] Greater HRV indicates a more resilient biological system that flexibly adjusts to changing demands and accordingly, is related to better physical and mental health. [39-43] Acute alcohol use reduces HRV; individuals with AUD have lower HRV than controls; [44] and HRV may be lower among heavy-drinking young adults compared to their non- or moderate-drinking peers. [45] Poor sleep may also reduce HRV. [46] The results of preliminary studies suggest that biofeedback interventions to improve HRV (i.e., paced breathing protocols) may reduce alcohol craving among individuals in substance use treatment or recovery programs. [47] HRV biofeedback may also have potential as an alcohol prevention/early intervention strategy, particularly receiving feedback about alcohol effects on HRV. This hypothesis has not been tested but users of this new PPG sensor technology reported reductions in drinking after observing negative effects of alcohol use on their health data. [48] PPG sensors and integrated mobile apps analyze user health and behavior data and can tailor health advice to these data, thereby creating a unique alcohol intervention opportunity. Thus, a controlled test of HRV/RHR/sleep monitoring and feedback on drinking via this new PPG technology warrants further study.

We will conduct the first controlled test of a personalized feedback intervention targeting HRV, RHR, and sleep for heavy-drinking young adults via PPG sensors and electronic daily diaries to provide preliminary data for a larger grant application. The study is directly responsive to NIAAA strategic directions focused on novel alcohol prevention and intervention efforts for young people. This innovative strategy could have great potential as it does not rely on self-identification for alcohol treatment, [9-12] targets important substance use risk factors (i.e., sleep, HRV), [25-31, 44, 47] is applicable for all young adults, is easily accessible, and uses technology, which appeals to young adults. [20-22]

We expect that a feedback intervention targeting HRV, RHR, sleep and their association with alcohol use will reduce drinking in young adults. The study will yield preliminary data for a larger, definitive study. The rich database will allow for an exploration of the links among these health variables to inform our understanding of their role in young adult AUD risk.

1.5 Potential Risks and Benefits

1.5.1 Potential Risks

The major potential risks in this study are related to intervention components, interviews/self-report questionnaires, urine collection, and recording of treatment exit interviews.

Intervention Components:

PPG sensor use and mobile self-monitoring of alcohol use and health behaviors poses minimal risk. There are no side effects from wearing the OURATM beyond minor inconvenience – users can shower and swim with the devices. OURATM deidentifies user data and will distribute data to us using deidentified data via a password-protected dashboard that protects participants' confidentiality. The brief health advice provided by the OURATM mobile app and our personalized alcohol-related feedback and advice pose minimal risk. A great deal of this information is also available to young adults through external health websites. Our experience providing brief alcohol and health interventions to young adults and cognitive-behavioral sleep interventions indicates that they are well tolerated. Our research group has several PhD-level clinical psychologists available for consultation should the need arise. Participants will be monitored regularly through daily diaries and via remote reminders regarding study procedures.

The Oura ring is a wearable ring that includes multiple sensors to detect several health biomarkers including temperature, sleep, heart rate and connects to mobile application that provides users with information about their health status. Participants will wear the device and half will have access to the mobile application to view their health data so we can test the effect of using this device and receiving this health information on drinking behavior. The device is not FDA approved and it is our understanding that they are not seeking FDA approval status at this time for any medical indications. The Oura ring is intended for general health self-monitoring and is available to the public.

These will only be given to participants and tested by research staff. They will be stored in a locked cabinet in a locked research office at CMHC in between use. The devices will also be cleaned in between use by different participants.

Interviews and Self-Reports:

Research interviews and assessments, including completing daily health diaries, are all non-invasive and should add no risk. The major disadvantage is the time it takes to complete them and possible breach of confidentiality. Our research group's experience with these measures indicates that they are acceptable to participants. [name], a licensed clinical psychologist, will be available to meet with individuals and will provide staff with consultation should the need arise. Careful efforts aimed at maintaining confidentiality will be made, which are described below, and only participants' study numbers will be recorded on the forms themselves in order to protect confidentiality.

Recording of Exit Interviews: Recording of interviews is necessary to evaluate participants' reactions to self-monitoring activities (i.e., daily electronic diaries and the OURAM smart ring) as well as personalized feedback and tailored health advice for those in the feedback group. To assure the confidentiality and protection of participants with respect to these procedures, the following steps will be taken:

- Participants have the right to refuse recording. Participants who consent to recording will be informed that they have the right to stop recording at any time.
- All recording will occur using ZOOM teleconferencing software, which is HIPAA-compliant and password-protected. Only [name], [name], or the Research Coordinator will record interviews.
- Interviews will be saved on a password protected secure server. Digital file names will only be identified by participants' study numbers.
- Access to digital recordings will be limited to key study personnel.

Effective screening will exclude all participants who would be at greater risk for complications from the intervention and/or study participation because of medical or specific psychiatric illnesses. [name], a licensed clinical psychologist, will evaluate all potential participants for inclusion regarding their psychiatric suitability. If participants are not eligible for the study and/or request further assistance with alcohol use, physical health, and/or sleep once the study is completed, appropriate referrals will be provided. Upon study enrollment, numerous safeguards will be used to monitor participants. Participants will receive at a minimum, weekly contact from Study Staff for reminders about study procedures/address any logistical problems with diaries, sensors, or other procedures. Plus, all participants will wear a sensor and complete daily diaries. Sensor data and diaries can be monitored remotely. [name] will be available to meet with participants and will provide participants with treatment referrals if they are interested.

Right to privacy for participation in this research will be protected through alphanumeric coding of data (in place of names) and proper storage of research records, including treatment exit interviews. Collected materials will be maintained via an alphanumeric reference system maintained by [name]. Participants' names will appear only on the consent form, the HIPAA authorization form, and a master list maintained in a physically locked file that is separate from research data. Our data collection and management procedures are fully compliant with HIPAA. Access will be limited to personnel intimately involved in the study. A Certificate of Confidentiality will also be obtained from the National Institutes of Health to protect access to the records. However, participants will also be told that if they present with suicidal or homicidal ideation and/or report any form of child/elder abuse or report plans to damage property then we will have to report this to the appropriate authorities and/or provide them with referrals for immediate treatment. Electronic data will be de-identified, and password protected. Only members of the study team will have access to the physical or electronic data. OURATM data are deidentified and are also protected through secure, password-protected servers. We will use an alphanumeric code to sign participants up to the OURATM mobile app in place of their names.

1.5.2 Potential Benefits

All participants will engage in self-monitoring that may help participants learn more about their alcohol use, health, and/or sleep. In this study, half of the participants will receive personalized feedback about their health and behaviors as well as tailored, evidence-based advice, which may help them improve their drinking, health, and/or sleep. All participants will be provided compensation for their participation. They will be able to withdraw from the study at any time. There is a need to reduce heavy alcohol consumption and alcohol-related risks among young adults. The purpose of this study is to test a mobile health intervention for heavy-drinking young adults. Mobile interventions that target young adults' other health concerns may provide alternative on ramps for intervening on alcohol use in this population. This study may help to engage more heavy-drinking young adults into treatment and reduce the substantial harms and healthcare costs associated with heavy alcohol use.

2 Study Purpose and Objectives

2.1 Hypothesis

Hypothesis 1: The *Feedback* group will report fewer total drinks consumed compared to the *Assessment* group. We will also examine secondary drinking outcomes: drinks per drinking day, % heavy drinking and abstinent days, alcohol-related consequences, and daily diary entries of alcohol use before bedtime.

Hypothesis 2: The *Feedback* group will have better self-reported PROMIS™ sleep quality ratings compared to the *Assessment* group. We will also examine secondary sleep outcomes: PROMIS™ sleep-related impairment ratings, sensor-derived quantitative sleep outcomes (i.e., duration, efficiency, awakenings, % of time in sleep stages, bed/wake times), and daily diary ratings of sleep quality

Hypothesis 3: The *Feedback* group will report greater HRV compared to the *Assessment* group. We will also examine RHR as a secondary outcome.

Hypothesis 4: *Feedback* will rate higher than *Assessment* on measures of intervention post-treatment ratings and interviews and use metrics.

2.2 Primary Objective

Aim 1: Examine condition effects on total drinks consumed over Weeks 2-10 (summarized over 4-week periods), controlling for baseline drinks.

2.3 Secondary Objective (if applicable)

Aim 2.1: Examine condition effects on PROMIS™ sleep quality and sleep-related impairment self-ratings, controlling for baseline, using mixed effects models.

Aim 2.2: To examine the preliminary efficacy of a PPG-sensor based HRV, RHR, sleep feedback intervention on HRV measured using sensor data.

Aim 2.3: To evaluate intervention feasibility and acceptability using subject post-treatment ratings and interviews and use metrics.

3 Study Design

3.1.1 General Design Description

Study Design

The purpose of this study is to test a mobile health intervention for young adults who report heavy alcohol use. The health intervention includes: (1) alcohol use and other health self-monitoring including use of a wearable biosensor, (2) a mobile application, and (3) personalized feedback and tailored health tips about your health and alcohol use data.

This study is the first controlled test of an HRV/RHR/sleep feedback intervention for heavy-drinking young adults (N=60; ages 18-25) and will take advantage of a marketed PPG sensor and mobile app, OURATM. Subjects will be randomly assigned to 1 of 2 conditions: (1) Assessment (n=30) or (2) Feedback (n=30). The Assessment group will not have access to the OURATM mobile app and will not receive any health feedback. The Feedback group will have access to the OURATM app and will receive feedback. The OURATM app provides daily summaries of HRV, RHR, and sleep that subjects can view on the app. In addition, every 2 weeks, we will send a written report via text/email that: (1) summarizes subjects' alcohol use and the links with their HRV/RHR/sleep data and (2) provides health advice tailored to this data.

Following intake, all subjects will wear the OURATM daily for 6 weeks and will complete daily electronic diaries of alcohol use and sleep. All subjects will then complete follow-ups at Weeks 6 and 10. We will use standardized assessments to measure alcohol consumption and consequences (TLFB, PROMIS™)[56, 57] and self-reported sleep outcomes (PROMIS™).[58] The OURATM will measure quantitative sleep outcomes, HRV, and RHR. Daily electronic diaries will measure sleep quality and alcohol use. The primary alcohol outcome will be TLFB total drinks consumed, a composite measure of drinking quantity/frequency sensitive to change in our young adult research [19] and other brief alcohol interventions for this population. [6, 7, 51] Secondary alcohol outcomes will examine other effects on drinking: TLFB % heavy drinking and abstinent days; drinks per drinking day; PROMIS™ alcohol-related consequences; and daily diary entries of alcohol use before bedtime. The primary sleep outcome will be PROMIS™ sleep quality ratings, sensitive to change in our young adult research. [19] Secondary sleep outcomes will include PROMIS™ sleep-related impairment ratings, OURATM quantitative sleep outcomes (i.e., duration, efficiency, latency, wakefulness, % time in sleep stages, bed/wake times) and sleep quality daily diary entries. The primary health outcome will be OURATM HRV due to its strong association with heavy drinking. [43, 44] OURATM RHR will be a secondary outcome. We will evaluate feasibility and acceptability with treatment-exit interviews and OURATM use metrics (below).

Eligible subjects will be randomized to: (1) Assessment or (2) Feedback. All subjects will begin wearing an OURATM right after intake and will complete daily diary assessments.

Assessment (A) (n=30): Subjects in this group will only monitor their health/behaviors and will not receive any health feedback or advice. They will wear the OURATM daily and complete daily electronic diaries about bedtime behaviors (e.g., amount/timing of alcohol use) and their sleep for 6 weeks. Diaries will be programmed in MEI Research and sent via a notification each morning, a successful procedure for our current R34-funded study.

Feedback (F) (n=30): Subjects in this group will monitor their health/behaviors and will receive health feedback and advice. Subjects will wear the OURATM daily and complete daily MEI Research diaries for 6 weeks. They will also have access to the OURATM mobile app. Subjects will receive the following daily health information from the OURATM app: (1) HRV, RHR, sleep (i.e., duration, efficiency, latency, sleep stages, timing, wakefulness), body temperature, respiratory rate, and physical activity (i.e., steps, calories burned); (2) composite scores from 0-100 (≥ 85 optimal) for "Sleep", "Activity", and "Readiness" (i.e., overall measure of recovery, based on HRV, that signals capacity to perform at physical,

mental, cognitive best); and (3) advice regarding optimal bedtime, activity progress, inactivity, and recovery. At intake, we will orient subjects to OURATM app health feedback and advice. At Weeks 2, 4, and 6, subjects will receive written reports sent via a text/email link that summarizes their alcohol use (e.g., drinks per week, # of heavy occasions, peak BAC) and the links between drinking and OURATM health outcomes as well as tailored advice for improving health, including evidence-based brief content for alcohol (e.g., standard drinks, low risk drinking guidelines, BAC feedback, controlled drinking tips) [40-42] and sleep (e.g., sleep hygiene, stimulus control). [19, 53, 54, 59, 60] We will derive these reports using the OURATM Teams dashboard and daily diaries; subjects will not have dashboard access.

3.1.2 Study Date Range and Duration

Study procedures will include: an initial, in-person intake appointment (Week 0), a 6- week intervention phase, and 2 follow-up visits (Weeks 6 and 10).

3.1.3 Number of Study Sites

Sites: Screening appointments will take place at the Connecticut Mental Health Center (CMHC) main campus or the Substance Abuse Treatment Unit, a satellite location of CMHC. The Yale School of Nursing Biobehavioral Laboratory is also available as a back-up space for appointments. Follow-up visits will be conducted virtually using ZOOM.

3.2 Outcome Variables

3.2.1 Primary Outcome Variables

Timeline Follow-back Interview (TLFB): Valid/reliable/standardized interview to obtain alcohol quantity/frequency estimates [56] for a 30-day period prior to enrollment in the study and monthly following intake for a total of 3 months. [51] Calendar prompts and memory aids (e.g., holidays) are used to facilitate accurate recall of substance use during the targeted period. We will derive the following 30-day summary variables for: total drinks, drinks per drinking day, % heavy and abstinent days.

PROMIS™ Alcohol Consequences: Valid/reliable measure of positive alcohol consequences. [57]

Brief Young Adult Alcohol Consequences Questionnaire (BYAACQ): Valid/reliable measure of negative alcohol consequences. [81]

Protective Strategies Questionnaire (PSQ): Valid/reliable measure of direct and indirect strategies for reducing alcohol consumption and consequences. [83]

Alcohol daily diaries: subjects will record the timing and amount of alcohol use before bedtime. [71]

Physical Fitness/Activity: Self-reported assessments with validity against objective measures. [74, 75]

Intervention Feasibility/Acceptability: OURATM use metrics; quantitative and qualitative ratings of OURATM and diary self-monitoring and health feedback/advice components using treatment evaluation surveys and exit interviews (e.g., ease of use, helpfulness, satisfaction, suggestions for improvement).

3.2.2

3.2.3 Secondary and Exploratory Outcome Variables (if applicable)

PROMIS™ Sleep-Related Impairment and Sleep Disturbance: Valid/reliable measures of perceived alertness, sleepiness, during waking hours and functional impairments due to sleep problems and perceived sleep quality/satisfaction and difficulty initiating/maintaining sleep. [58]

Sleep daily diaries: subjects will rate their sleep quality upon waking.[72]

PROMIS™ Positive Affect/Depression/Anxiety: Valid/reliable measures of well-being, negative affect.[57, 73]

Physical Fitness/Activity: Self-reported assessments with validity against objective measures. [74, 75]

Morningness/Eveningness (ME) Questionnaire: Valid/reliable measure for degree of alertness during different points in the day. [80]

Munich ChronoType Questionnaire (MCTQ): Valid/reliable measure for how individuals sleep and wake. [80]

Theory of Planned Behavior (TPB): Valid/reliable measure for predicting risky drinking behavior. [78,79]

Dietary Screening Questionnaire (DSQ): Valid/reliable measure of dietary intake. [82]

COVID-19 Experiences Questionnaire: Self-report assessment to measure the impact of COVID-19. [84]

Intervention Feasibility/Acceptability: OURATM use metrics; quantitative and qualitative ratings of OURATM and diary self-monitoring and health feedback/advice components using treatment evaluation surveys and exit interviews (e.g., ease of use, helpfulness, satisfaction, suggestions for improvement).

3.3 Study Population

Participants: We will recruit both male and female heavy-drinking (report alcohol use that exceeds NIAAA recommended daily drinking limits (i.e., ≥ 5 for men; ≥ 4 for women) at least 4 times within the last 28 days at baseline but do not meet criteria for a severe alcohol use disorder) young adults (N=60; ages 18-25 years old) from the local community through online advertising/social media (e.g., Facebook, Instagram, Snapchat) and flyers and notices displayed around the local community and college campuses.

3.3.1 Number of Participants

Targeted for enrollment at Yale for this protocol: 60 subjects (Assessment group [n=30] and Feedback group [n=30]).

3.3.2 Eligibility Criteria/Vulnerable Populations

Prospective participants will be screened on initial eligibility criteria via a web-based screener on the study website. Our research group has successfully recruited participants, including heavy-drinking young adults utilizing these recruitment strategies.

Following completion of the pre-screener, research staff will contact potential subjects and inform them of their initial eligibility status. Those who meet initial criteria will attend an intake to provide written informed consent and complete final screening for inclusion/exclusion criteria. Eligible individuals will be randomized to their condition to begin immediately after intake.

All research staff and research participants will be screened for COVID-19 symptoms prior to entry into CMHC. These include: fever of 99.9°F or higher, cough, shortness of breath/difficulty breathing, fatigue, repeated shaking with chills, muscle pain or body aches, chills, headache, sore throat, new loss of taste or smell, congestion or runny nose, nausea or vomiting, or diarrhea. Research staff and research participants must additionally affirm that they have not been in close

proximity to anyone who is experiencing symptoms, or who have tested positive for COVID- 19, within 14 days of a scheduled in-person visit. Research staff and research participants will indicate whether they have traveled anywhere outside of Connecticut within 14 days prior to a scheduled in-person visit. Current Connecticut state guidance on quarantine requirements for those traveling into Connecticut from other states in the USA, or internationally, will be observed. This section will be updated as Connecticut and Yale guidelines change.

Inclusion Criteria:

- (1) 18-25 years of age
- (2) report ≥ 4 heavy drinking occasions in the past 28 days (i.e., ≥ 5 drinks on 1 occasion for men; ≥ 4 for women)
- (3) report Alcohol Use Disorders Identification Test – Consumption (AUDIT-C) scores indicative of risk of drinking harm (i.e., ≥ 7 for men; ≥ 5 for women) [70]
- (5) English speaking
- (6) have a smartphone for syncing OURAM™ data and receiving OURAM™ feedback. *An estimated 96% of young adults own a smartphone.*[76]

Exclusion Criteria:

- (1) history of a sleep disorder
- (2) night or rotating shift work; travel beyond 2 time zones in month prior and/or planned travel >2 time zones during study participation
- (3) clinically severe AUD in past 12 months defined by: a) history of seizures, delirium, or hallucinations during alcohol withdrawal; b) report drinking to avoid withdrawal symptoms or have had prior alcohol withdrawal treatment; c) required medical treatment of alcohol withdrawal in the past 6 months which is concluded through a clinical interview with either [name] or [name].
- (4) currently enrolled in alcohol or sleep treatment
- (5) current, severe psychiatric illness (i.e., bipolar disorder, schizophrenia, panic disorder, borderline personality disorder, organic mood or mental disorders, or suicide or violence risk) by history or exam which is verified by clinical interview with either [name] or [name].
- (6) current DSM-V substance use disorder as obtained by clinical interview with either [name] or [name]

No fetuses, neonates, pregnant women, children, prisoners, institutionalized individuals, or others who may be considered vulnerable populations will be included.

4 Study Methods/Procedures

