We will recruit heavy-drinking young adults (N=60; ages 18-25 years old) from the local community through online advertising/social media (e.g., Facebook, Instagram, Snapchat) and flyers and notices displayed around the local community and college campuses.

Subjects will be randomly assigned to 1 of 2 conditions: (1) Assessment (n=30) or (2) Feedback (n=30).

Urine Drug Toxicology: JANT Pharmaceuticals rapid urine drug test kit for opiates, cocaine, barbiturates, amphetamines, benzodiazepines, or phenylcyclidine. Positive tests are an exclusion criterion.

Breath Alcohol Concentrations (BAC): Subjects need to test negative on a handheld breathalyzer- an Alcohol-Sensor III (Intoximeter Inc., St. Louis, MO). Participants need to test negative to provide consent at intake and need to test $< .04\%$ at subsequent in-person treatment and assessment visits.

Number of Participants

Targeted for enrollment at Yale for this protocol: 60 subjects (Assessment group [n=30] and Feedback group [n=30]). This is a preliminary study, which if promising will lead to a larger trial of this intervention approach. Sample size estimates were based on enrolling a sufficient number of participants to determine the feasibility, acceptability, and preliminary efficacy of this PPG-sensor based feedback and brief advice intervention for reducing drinking among heavy-drinking young adults. This number is feasible to recruit for a 2-year study. Moreover, for Phase 1 psychotherapy intervention studies, the minimum recommended sample size is 15-30 subjects per group.

Study Schedule

There are 3 expected visits: an initial, in-person intake appointment (Week 0), a 6- week intervention phase, and 2 follow-up visits (Weeks 6 and 10).

Protocol Revision History

Include the IRB approved protocol version number and date for each revision of the protocol. All version history should remain in the table and never be deleted. The oldest IRB approved version of the protocol should be listed on the top row. The most recent IRB approved version should be listed on the bottom row.

Version Date	Summary of Substantial Changes
Version 2, 4/21/2021	Accepted tracked changes, included description of http://www.clinicaltrials.gov , included Oncore usage for payment, clarified clinical interviews will be conducted by licensed experts to determine if participant meets any exclusion criteria, and clarified that consenting process will occur at either in person or remotely.

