4.4.4 Analysis of Subject Characteristics (if applicable)

We will use descriptive statistics were used to summarize frequencies and percentages of sociodemographic characteristics (age, race, ethnicity, gender, college status) and clinical characteristics (drinking, sleep, and other health behaviors).

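### Does exclusion (6), which makes no exception for alcohol, contradict the rule that only severe alcohol use disorder is barred?

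*Combined protocol and SAP*

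**What the plan says.** Four places in the combined protocol and SAP bear on AUD at entry.

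- **Section 3.3, Study Population.** It describes the people to be recruited as heavy drinkers aged 18-25 who "do not meet criteria for a severe alcohol use disorder".
- **Section 3.3.2, exclusion (3).** It bars "clinically severe AUD in past 12 months defined by: a) history of seizures, delirium, or hallucinations during alcohol withdrawal". Limb (b) covers people who "report drinking to avoid withdrawal symptoms or have had prior alcohol withdrawal treatment", and limb (c) those who "required medical treatment of alcohol withdrawal in the past 6 months". This is the only definition of severe AUD in the document.
- **Section 3.3.2, exclusion (6).** It bars a "current DSM-V substance use disorder as obtained by clinical interview", the interview being held by either of two designated interviewers. It has no severity threshold and no exception for alcohol.
- **Synopsis, Study Population.** A positive result on a "rapid urine drug test kit for opiates, cocaine, barbiturates, amphetamines, benzodiazepines, or phenylcyclidine" is also an exclusion. Alcohol is not on that panel.

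Section 4.1.1 has a licensed clinical psychologist give the M.I.N.I. at intake. Section 4.4.4 plans a descriptive summary of "clinical characteristics (drinking, sleep, and other health behaviors" and similar items, without naming AUD status.

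**The concern.** Suppose a candidate meets the heavy-drinking and AUDIT-C inclusion criteria, has a current AUD short of severe, and has no withdrawal history. Section 3.3 and exclusion (3) do not bar this person. Exclusion (6), read word for word, does, because AUD is a substance use disorder. In a trial that recruits on at least 4 heavy drinking occasions in 28 days, such candidates are to be expected.

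The reading applied decides who enters, how fast recruitment goes, and which population the pilot's effect estimates describe. Section 4.4.2 says those estimates will inform a more definitive study. If the report did not give AUD status, a reader might not know which reading had been used. Exclusion (3) adds a second untidiness: its opening words set a 12-month window, limbs (a) and (b) carry no date, and limb (c) uses 6 months.

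**Working it through.** No figure in the plan depends on this point, so there is nothing to recompute. The check sets the rules side by side and asks whether both readings of (6) can be followed.

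**Step 1: how the rules combine.** A candidate is eligible only if every inclusion criterion is met and no exclusion applies. Not being barred by (3) is therefore different from being admitted. Section 3.3 does not promise admission either. It is silent on sleep disorders, shift work, current treatment and psychiatric illness, all of which exclude under Section 3.3.2, so it cannot be a complete test for entry.

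**Step 2: apply each reading of (6).**

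| | (6) includes alcohol | (6) means other substances |
|---|---|---|
| Current AUD, less than severe, no withdrawal features | Barred by (6) | Not barred |
| AUD meeting exclusion (3) | Barred | Barred by (3) |
| Heavy drinker, no AUD | Not barred | Not barred |
| Section 3.3 condition met by all enrolled, with severe AUD defined as in (3) | Yes | Yes |
| Does (3) still have a function? | Yes: it looks back 12 months, (6) covers only current disorder | Yes: it is the only AUD rule |

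The two columns differ in one row. Within each column no rule contradicts another.

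**Step 3: what the text suggests was meant.** Three features point to other substances. Alcohol has its own criterion with its own severity limit. Limiting Section 3.3 to severe AUD would do little for current disorder if every current AUD were already barred. The urine panel covers only other drugs. One feature points the other way: Section 3.2.1 describes the alcohol Timeline Followback as recall of substance use, so the protocol's vocabulary does not keep alcohol outside that term. The balance favours other substances, but the text does not settle it.

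**Step 4: what reaches the analysis.** Sections 3.3.2 and 4.1 place the final eligibility decision before randomization. AUD status is therefore a baseline feature, and either reading restricts both arms in the same way. The target stays at 60, 30 per arm. Section 4.4.2 states 80% power at a two-sided 0.05 level for a large difference and gives no standard deviation or number of drinks, so no input to that statement changes with the reading. The mixed model in Section 4.4.3 adjusts for baseline drinks and includes sex; it has no term for AUD.

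**Step 5: the look-back wording in (3).** Take someone treated for withdrawal 18 months before intake. The opening 12-month window leaves this person out of the exclusion, while limb (b), taken without a date, brings them in. This question lies inside (3) and does not depend on (6). Reading the opening window as governing the limbs is workable. Like (6), it is decided at interview before randomization.

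**The case for a change.** The strongest case for acting has three parts.

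First, a pilot's estimates are useful only if the population is defined, and whether people with AUD are included is a basic descriptor in an alcohol trial. That is fair. It concerns description, however, and the M.I.N.I. is done on everyone at intake. Section 4.4.4 does not name AUD status, but its clinical characteristics leave room for it, and an analyst would ordinarily report it.

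Second, Section 5.4 treats any noncompliance with the protocol as a deviation, to be reported within 2 working days. Under the literal reading each participant enrolled with a mild AUD would be a deviation; under the other reading none would. This is a real loose end for a monitor. It is settled by the investigator stating which reading the interviewers apply, and it leaves the estimates and tests as they are.

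Third, it can be argued that Section 3.3 and exclusion (3) disagree about a person judged severe without any withdrawal feature or treatment. That argument needs a second standard of severity, which the protocol never states. Exclusion (3) supplies the only definition, and Section 3.3 reads naturally as shorthand for it.

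What stands is that the text does not say whether (6) covers alcohol, and that the time windows in (3) are mixed. Both are matters of wording.

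**Conclusion.** This is a gap in wording that the study team can fill sensibly, and no change to the plan follows. Exclusion (6) leaves its scope over alcohol unstated, but each reading yields a coherent eligibility list and a sound randomized comparison in 60 heavy drinkers without severe AUD as exclusion (3) defines it. The effect on sample size, stated power and bias between arms is nil. The effect on recruitment and on the breadth of the population is real in principle. It cannot be sized, because the documents give no AUD prevalence for these candidates.

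The conclusion rests on three assumptions. Eligibility is settled before randomization, as Sections 3.3.2 and 4.1 say. The two designated interviewers apply one reading throughout. Severe AUD in Section 3.3 means what exclusion (3) defines. If the interviewers differed, the sample would be more mixed, but the arms would still be comparable because assignment comes afterwards. Stating the intended reading, aligning the look-back periods or listing AUD status at baseline would be harmless tidying, and no result depends on it. This review takes no position on which eligibility rule is clinically right.
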